4.5.1. Adverse Events and Serious Adverse Events

An AE is any untoward medical occurrence in a patient administered a study drug which may or may not have a causal relationship with the study drug. Therefore, an AE is any unfavorable and unintended sign (including abnormal laboratory finding), symptom, or disease which is temporally associated with the use of a study drug, whether or not considered related to the study drug.

An AE also includes any worsening (ie, any clinically significant change in frequency and/or intensity) of a pre-existing condition that is temporally associated with the use of the study drug.

The investigator (or designee) will seek information on AEs at each patient contact and record all AEs that occur from the time the informed consent is signed until 90 days after the last dose of study drug. Prior to initiation of study drug, only the following categories of AEs should be reported on the AE eCRF:

- SAEs
- Non-SAEs associated with a protocol-mandated intervention (eg, AEs related to an invasive procedure such as a biopsy)

Other AEs that occur prior to first treatment should be reported on the medical history eCRF.

All AEs after initiation of study drug and until 90 days after the last dose of study drug, regardless of relationship to study drug, will be reported on the AE eCRF. Additionally, any SAE or other AE of concern that the investigator believes may be related to study drug and that occurs later than 90 days after last study drug should be reported.

Pre-treatment AEs are defined as AEs that developed or worsened during the pre-treatment period.

Treatment-emergent AEs (TEAEs) are defined as AEs that developed or worsened during the on-treatment period and any treatment-related AEs that occur during the post-treatment period but prior to patients receiving their first dose of cemiplimab as adjuvant therapy or another anticancer systemic therapy.

Post-treatment AEs are defined as AEs that developed or worsened during the post-treatment period and are not considered drug related by the investigator.

All adverse events are to be coded using Medical Dictionary for Regulatory Activities (MedDRA).

The severity of AEs (including test findings classified as AEs) will be graded using the NCI-CTCAE v5. Adverse events not listed in the NCI-CTCAE v5 will be graded according to the following scale (Table 2):

Table 2: Grading System for Adverse Events Not Listed in NCI-CTCAE

Grade	Severity	Description
1	Mild	Asymptomatic or mild symptoms; clinical or diagnostic observations only; intervention not indicated.
2	Moderate	Minimal, local, or noninvasive intervention indicated; limiting age-appropriate instrumental ADL*.
3	Severe	Severe or medically significant but not immediately life-threatening; hospitalization or prolongation of hospitalization indicated; disabling; limiting self-care ADL**.
4	Life-threatening	Life-threatening consequences; urgent intervention indicated.
5	Death	Death related to AE

* Instrumental Activities of Daily Living (ADL) refer to preparing meals, shopping for groceries or clothes, using the telephone, managing money, etc.

** Self-care ADL refer to bathing, dressing and undressing, feeding self, using the toilet, taking medications, and not bedridden.

The relationship of AEs to study drug will be assessed by the investigator and be determined based on protocol specified criteria.

Laboratory results, vital signs, or ECG abnormalities are to be recorded as AEs if they are medically relevant: symptomatic, requiring corrective therapy, leading to treatment discontinuation and/or fulfilling a seriousness criterion.

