8.3.3. Immune-related Adverse Events and Study Drug Discontinuation

8.3.3.1. Identification of Immune-Related Adverse Events

Investigators must be extremely vigilant and be ready to intervene early in the management of irAEs, as the onset of symptoms of irAEs (eg, pneumonitis) may be subtle. An irAE can occur shortly after the first dose or several months after the last dose of treatment. All AEs of unknown

etiology associated with drug exposure should be evaluated to determine possible immune etiology. If an irAE is suspected, efforts should be made to rule out neoplastic, infectious, metabolic, toxin, or other etiologic causes prior to labeling an AE as an irAE.

Based on the emerging safety profile of cemiplimab and other antibodies targeting the PD-1/PD-L1 axis, working case definitions are provided in the Investigator's Brochure to help investigators distinguish irAEs from non-immune AEs commonly associated with PD-1 inhibition (Naidoo, 2015)(Weber, 2015). This is not exhaustive of all possible irAEs. Clinical presentations of less common irAEs, including neurologic, musculoskeletal, cardiac, renal, and ocular events (Hoffman, 2016)(Zimmer, 2016), should be reviewed in patients with concerning presentations.

The case definitions in the Investigator's Brochure have not been validated and are intended only as guidance for investigators to help distinguish irAEs from non-immune AEs. These definitions may evolve as clinical experience increases with cemiplimab and other antibodies targeting the PD-1/PD-L1 axis. Investigators' clinical judgment may include other factors when determining immune-relatedness.

Adverse events that meet the criteria for irAEs, as noted above in the Investigator's Brochure, should be reported as irAEs in the eCRF. If AEs corresponding to the common terms for irAEs are attributed as NOT related to cemiplimab by the investigator, additional information should be provided to substantiate an alternative attribution (eg, infectious diarrhea).

If not provided at the outset, this information may be requested by immediate edit checks or in subsequent queries. The sponsor may request additional information for any AE that is of a type known to be potentially immune-related (eg, rash, colitis, elevated transaminases, endocrine), but is deemed not an irAE by the investigator.

Any grade 3 or greater irAE should be reported as an adverse event of special interest (AESI) (Section 10.4.3).

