8.7.2. Permitted Medications and Procedures

The following medications and procedures will be permitted, under the following conditions:

- Any medication required to treat an AE and/or irAE, including systemic corticosteroids
- Systemic corticosteroids for physiologic replacement (even if >10 mg/day prednisone equivalents)
- A brief course of corticosteroids for prophylaxis or for treatment of non-autoimmune conditions
- Oral contraceptives, hormone-replacement therapy, or other maintenance therapy may continue
- Acetaminophen at doses ≤ 2 g/day
- Surgical resection of pre-malignant lesions or basal cell carcinoma (BCC) lesions
- Other medications and procedures may be permitted on an individual basis by the investigator and in consultation with the sponsor
- Radiation therapy (with concurrent anti-cancer cytotoxic chemotherapy therapy and/or epidermal growth factor receptor-directed therapy) is permitted in the adjuvant portion of the study, at the discretion of the investigator. Such patients will be followed for disease recurrence but will not receive further cemiplimab on study.

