10.4. Recording and Reporting Adverse Events

10.4.1. Adverse Events

The investigator (or designee) will seek information on AEs at each patient contact and record all AEs that occur from the time the informed consent is signed until 90 days after the last dose of study drug. Prior to initiation of study drug, only the following categories of AEs should be reported on the AE eCRF:

- SAEs
- Non-SAEs associated with a protocol-mandated intervention (eg, AEs related to an invasive procedure such as a biopsy)

Other AEs that occur prior to first treatment should be reported on the medical history eCRF.

All AEs after initiation of study drug and until 90 days after the last dose of study drug, regardless of relationship to study drug, will be reported on the AE eCRF. Additionally, any SAE or other AE of concern that the investigator believes may be related to study drug and that occurs later than 90 days after last study drug should be reported.

Information on follow-up for AEs is provided in Section 10.4.6. Laboratory, vital signs, or ECG abnormalities are to be recorded as AEs as outlined in Section 10.4.5.

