4.5. Safety Variables

Patient safety will be assessed through the collection of reported adverse events (AEs), clinical laboratory data, vital signs, ECG, and physical exam.

The observation period will be divided into three segments: pre-treatment, on-treatment and post-treatment.

- The pre-treatment period is defined as the time from signing the ICF to before the first dose of study drug.
- The treatment period is defined as the time from the day of first dose of neoadjuvant cemiplimab to the day of the last dose of neoadjuvant cemiplimab plus 90 days or to 1 day before patients receive their first dose of adjuvant cemiplimab or another anticancer systemic therapy, whichever is earlier.
- The post-treatment period is defined as the time starting one day after the end of on treatment period.

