6.3. Data Handling Convention for Missing Data

No missing data imputation is planned in this study unless specified otherwise.

For categorical variables, patients with missing data are not included in calculations of percentages unless otherwise specified. When relevant, the number of patients with missing data is presented.

Medication missing/partial dates

To determine whether a medication is prior, concomitant or post-treatment medication, the missing medication start date is estimated as early as possible up to date of the first study treatment, and the missing medication end date is estimated as late as possible. If the medication start date is missing, the onset day will not be imputed in medication listings.

Date of first / last study treatment

Date of first infusion is the first non-missing start date of dosing filled in the CRF “Investigational Product” module.

AE suspected to be caused by cemiplimab

If AE suspected to be caused by cemiplimab is missing, the AE relationship will be imputed as related.

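### In patients given only neoadjuvant cemiplimab, non-serious cemiplimab-related AEs that start on or after another systemic anticancer therapy fit no AE class and no described summary table

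*SAP*

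**What the plan says.** SAP 4.5 splits observation into pre-treatment, on-treatment and post-treatment periods. The on-treatment period runs from the first neoadjuvant dose to 90 days after the last neoadjuvant dose, or "to 1 day before patients receive their first dose of adjuvant cemiplimab or another anticancer systemic therapy, whichever is earlier".

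SAP 4.5.1 then sorts AEs. A TEAE is any AE that develops or worsens on treatment, plus treatment-related AEs "during the post-treatment period but prior to patients receiving their first dose of cemiplimab as adjuvant therapy or another anticancer systemic therapy". The third class is narrower: "Post-treatment AEs are defined as AEs that developed or worsened during the post-treatment period and are not considered drug related by the investigator". The synopsis and Protocol 11.5.5.1 carry the same TEAE rule. The restriction of post-treatment AEs to unrelated events appears only in the SAP.

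Collection does not stop at a new therapy. Protocol 10.4.1 requires reporting of "All AEs after initiation of study drug and until 90 days after the last dose of study drug, regardless of relationship to study drug". After 90 days it asks only for SAEs or other AEs of concern that the investigator thinks may be related.

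SAP 5.7.1 describes its neoadjuvant tables in terms of TEAEs: related, serious and fatal TEAEs, TEAEs leading to discontinuation, and treatment-emergent irAEs. The AESI and infusion-reaction bullets sit in the same TEAE list. A separate summary covers AEs from the first adjuvant cemiplimab dose to 90 days after the last.

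**The concern.** The TEAE and post-treatment classes appear meant to divide late events between them, with related events in the first and unrelated events in the second. The cut at another systemic therapy breaks that division on the related side only. A cemiplimab-related event that starts after the cut is recorded but belongs to no class, and the TEAE-based tables leave it out.

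The plan itself creates patients in this position. Protocol 8.7.2 says: "Radiation therapy (with concurrent anti-cancer cytotoxic chemotherapy therapy and/or epidermal growth factor receptor-directed therapy) is permitted in the adjuvant portion of the study". Protocol 9.1.6 rules out adjuvant cemiplimab for anyone given adjuvant radiation, so the adjuvant AE summary cannot pick these patients up. Patients who start systemic treatment after progression, incomplete resection or recurrence, without having had adjuvant cemiplimab, are in the same position.

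The protocol also expects late toxicity: "An irAE can occur shortly after the first dose or several months after the last dose of treatment". The safety profile of neoadjuvant cemiplimab is a secondary objective, and what is at stake is the completeness of its related-AE, irAE and AESI tables.

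**Working it through.** The plan gives no figure for this point, so the check applies the definitions to test events and then counts the days affected.

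**Rules (SAP 4.5, 4.5.1, 5.7.1).** Let L be the day of the last neoadjuvant dose and S the day another systemic therapy starts.
- The on-treatment period ends at the earliest of L + 90, S − 1, and the day before the first adjuvant cemiplimab dose.
- An AE is a TEAE if it starts on treatment, or if it is related and starts later but before both S and the first adjuvant dose.
- An AE is a post-treatment AE if it starts after the on-treatment period and is unrelated.
- The adjuvant summary covers the first adjuvant dose to the last adjuvant dose + 90 days.

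**Test events, with L = day 64.**

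| Event | TEAE | Post-treatment AE | Adjuvant summary |
|---|---|---|---|
| Related, day 130; chemoradiation from day 115 | no | no | no |
| Related, day 170; chemoradiation from day 115 | no | no | no |
| Unrelated, day 130; chemoradiation from day 115 | no | yes | no |
| Related, day 130; radiation alone or observation | yes | no | no |
| Related, day 170; no new systemic therapy | yes | no | no |
| Related, day 320; adjuvant cemiplimab days 136 to 262, chemotherapy from day 300 | no | no | yes (262 + 90 = day 352) |

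The first two rows show the gap. The fourth shows that the same related event on the same day is a TEAE if the patient had radiation without a systemic agent. The last shows that a patient on adjuvant cemiplimab is covered until 90 days after the last adjuvant dose. The day-170 events lie beyond L + 90 = day 154, so they are reported only if they are SAEs or AEs of concern.

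**Days affected.** Days of the 90-day window removed = (L + 90) − (S − 1) = 91 − (S − L). The documents do not say when chemoradiation would start. I assume the EOT1 visit, which Table 2 of the protocol places 30 ± 10 days after surgery. The last dose is on day 64 ± 3 and surgery on day 85 (window 75 to 100).
- Nominal: S = 85 + 30 = 115, so 91 − (115 − 64) = 40 days (days 115 to 154), and 40/90 = 44%.
- Fewest: L = 61, surgery on day 100, EOT1 40 days later. S = 140, so 91 − 79 = 12 days.
- Most: L = 67, surgery on day 75, EOT1 20 days later. S = 95, so 91 − 28 = 63 days.
- If surgery is exactly 21 days after the last dose, as the surgery footnote to Table 2 intends, S − L runs from 41 to 61, giving 50 down to 30 days.

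These figures assume four doses. For a patient who stops early the same formula applies, but the documents give no L or S to put in.

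**Effect on a reported rate.** With 76 treated patients, one omitted patient lowers an incidence by 1/76 = 1.3 percentage points.

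**The case against.** The strongest reply is that the cut is a deliberate attribution rule. Once another anticancer drug is on board, a late event may be due to that drug, and the synopsis, Protocol 11.5.5.1 and the SAP all state the TEAE rule the same way. This stands as a reason to keep such events out of the TEAE tables. It does not justify leaving them out of every table, because these are events that the investigator attributed to cemiplimab.

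A reader might infer that all late related harm in these patients goes unreported. The documents do not support that.
- Protocol 11.5.5.1 lists and summarises deaths and other SAEs with no TEAE limit, and SAP 1.2.4 does not name this among its departures from the protocol. SAP 5.7.1 mentions only serious and fatal TEAEs, so the two documents need aligning, but the protocol output has not been withdrawn.
- The same protocol section says that the terms of all reported AEs will be listed, so individual records should remain traceable.
- AESIs, serious or not, go to the sponsor within 24 hours (Protocol 10.4.3). Surveillance is intact, and the gap is one of tabulation.

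A reader might also think that the missing-data rule makes matters worse, since SAP 6.3 says: "If AE suspected to be caused by cemiplimab is missing, the AE relationship will be imputed as related". It does not. The SAP describes no table of post-treatment AEs, so an event after new therapy would be untabulated even if classed as unrelated. Before new therapy, the imputation moves late events into the TEAE tables. For the same reason, the contrast with unrelated events on the same day concerns classification and changes no described output.

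**Conclusion.** The gap is real and follows from the wording alone. In neoadjuvant-only patients, a cemiplimab-related AE with onset on or after another systemic anticancer therapy is neither a TEAE nor a post-treatment AE. If it is non-serious, it reaches no summary table that either document describes. That includes non-serious irAEs of grade 3 or higher, which the protocol treats as AESIs.

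The effect is limited. Where therapy starts at EOT1, 40 of the 90 days after the last dose are affected on the nominal schedule, and 12 to 63 days over the visit windows. The start day is an assumption. The documents give neither the share of patients who would receive systemic therapy without adjuvant cemiplimab nor an expected rate of late related events, so no count of missing events can be derived. It is probably small, because a patient must have a systemic agent, no adjuvant cemiplimab and a late, non-serious related event. The primary endpoint is untouched. This is a cheap correction worth making before database lock.

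**What to change.** 1. Keep the TEAE definition as it stands, so that the synopsis, Protocol 11.5.5.1 and the SAP stay consistent.
2. In SAP 4.5.1, add a class for cemiplimab-related AEs with onset on or after the start of another anticancer systemic therapy. Alternatively, remove from the post-treatment definition the condition that limits it to AEs not attributed to the drug.
3. In SAP 5.7.1, add one separate table and listing of related AEs, irAEs, AESIs and SAEs in that class. Step 2 alone would not be enough, because the SAP describes no table for post-treatment AEs.
4. Bring SAP 5.7.1 into line with Protocol 11.5.5.1 on deaths and SAEs, or declare the difference in SAP 1.2.4.

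The cost is a few lines of SAP text and one extra table. No new data are needed. Some of the tabulated events may be partly due to the later therapy, which is why they should stay apart from the TEAE tables.

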4.5.2. Adverse Events of Special Interest

All adverse events of special interest (AESI), serious and non-serious, must be reported within 24 hours of identification. Adverse events of special interest for this study include the following:

- Grade 2 or higher infusion-related reactions (IRRs)
- Grade 3 or higher immune-related toxicities (irAE)

4.5.3. Laboratory Safety Variables

The clinical laboratory data consists of serum chemistry, hematology, urinalysis, pregnancy testing, and other. Clinical laboratory values will be converted to standard international (SI) units and grouped by function in summary tables. Conventional unit may be provided. Detailed tests and time are described in the Protocol.

4.5.4. Vital Signs

Vital signs, including temperature, sitting blood pressure, pulse, and respiration will be collected according to the Protocol.

4.5.5. 12-Lead Electrocardiography (ECG)

A standard 12-lead ECG will be performed at time points according to the Protocol. The ECG strips or reports will be retained with the source. The ECG will be reviewed by the investigator (paper or electronic tracing) and will be available for comparison with subsequent ECGs by the investigator: RR interval (sec), PR Interval (msec); QRS Interval (msec); QT Interval (msec); Heart Rate (beat per minute; recorded from the ventricular rate)

Any ECG finding that is judged by the Investigator as a clinically significant change (worsening) compared to the screening value will be considered an AE, recorded, and monitored.

4.5.6. Physical Examination Variables

A complete or limited physical examination will be performed at visits specified in the Protocol. Care should be taken to examine and assess any abnormalities that may be present, as indicated by the patient's medical history.

Complete physical examination will include examination of head and neck, lungs, heart, abdomen, lymph nodes, extremities, and skin. A brief neurologic examination also should be performed.

Limited physical examination will include lungs, heart, abdomen, and skin.

4.6. Anti-Drug Antibody Variables (ADA)

The immunogenicity variables are ADA status, dose titer, and time-point/visit. Samples in this study will collected at the clinic visits specified in the Protocol.

5. STATISTICAL METHODS

For continuous variables, descriptive statistics will include the following: the number of patients reflected in the calculation (n), mean, median, standard deviation, minimum, and maximum. In addition, 25th percentile and 75th percentile will be provided.

For categorical or ordinal data, frequencies and percentages will be displayed for each category.

For time-to-event variables, median time-to-event (and the survival rate at a fixed time point) and its two-sided 95% confidence intervals will be summarized by the Kaplan-Meier method, unless otherwise specified.

The primary analysis will be performed when all patients have completed surgery or deemed no longer a candidate for surgery after treatment with neoadjuvant cemiplimab. An updated analysis will be provided after all patients have completed post-treatment follow-up or end of study.

5.1. Demographics and Baseline Characteristics

Demographic and baseline characteristics will be summarized descriptively.

5.2. Medical History

Medical history will be summarized by SOC and PT and will be sorted by decreasing frequency of SOC followed by PT.

Prior cancer related surgery will be summarized by prior surgery status. Prior cancer related systemic therapy will be summarized by systemic therapy type. Prior cancer related radiotherapy will be summarized by prior radiotherapy status.

5.3. Prior/concomitant Illnesses and Medications

Prior/concomitant medications and procedures will be summarized based on SAF.

The number and proportion of patients taking concomitant medications will be summarized, sorted by decreasing frequency of ATC Level 2 and ATC Level 4. Concomitant procedures will be summarized by SOC and PT.

5.4. Subject Disposition

Subject disposition will be summarized. The following summaries will be provided:

- The total number of screened patients
- The total number of enrolled patients
- The total number of enrolled but not dosed patients
- The total number of patients in each analysis set
- The total number of patients who discontinued from study drug, and the reasons for discontinuation

- The total number of patients who discontinued the study, and the reasons for discontinuation

